### **3.7.2.2 Clinical Assessments**

Clinical status assessment must be performed predose on Day 1. It is preferred that clinical status assessments be performed predose during subsequent visits. Clinical assessments will be performed per inpatient standard of care and should include review of subject chart entries, including hyponatremia assessment notes, trial- and nontrial-specific laboratory results, any examination findings, medical problem list changes, and fluid intake and output to evaluate overall subject eligibility in terms of hyponatremia state. The clinical assessment will focus on symptoms and signs which will inform treatment decisions (eg, the need to switch to rescue therapy, or the ability to safely discharge a subject from the hospital). The clinical assessment should be

performed by a trial investigator who will be aware of laboratory and other clinical response data.

### **3.7.2.3      Quality of Life Assessments**

Two patient-reported outcomes instruments (acute versions with 7 day recall period) will be used to assess subject quality of life: PedsQL Generic Core Scale and PedsQL Multidimensional Fatigue Scale. Both instruments are appropriate for  $\geq 2$  years of age, however availability may be limited for certain ages and languages. The age groups covered by these assessments are Toddler (2–4 years), Young child (5–7 years), Child (8–12 years), and Adolescent (13–18 years). Depending on the subject's age, the questionnaire may be completed by either the subject, subject and parent/caregiver, or the parent/caregiver, as appropriate.

The PedsQL Generic Core Scale consists of 23 items encompassing physical, emotional, social, and school domains.

The PedsQL Multidimensional Fatigue Scale consists of 18 items in 3 subscales: general fatigue, sleep/rest fatigue, and cognitive fatigue. The instrument focuses on the domains of processing speed, attention/vigilance, visual and working memory.

The assessment time points are at screening, Day 4 and 7 days post-last dose.

## **3.7.3      Pharmacokinetic/Pharmacodynamic Assessments**

### **3.7.3.1      Pharmacokinetic Assessments**

#### **3.7.3.1.1      Blood Collection Times**

Blood samples will be taken so that tolvaptan and metabolite concentrations can be determined. Samples will be taken at the following times:

- On Day 1 at 2 hours ( $\pm 5$  minutes) and 8 hours (concurrent with 8 h serum sodium sample) post-first dose.
- On Days 1, 2, 3, and 4 samples will be taken at trough ( $24 [\pm 4]$  hours post-previous dose) (prior to the subsequent dose), concurrent with serum sodium samples, for subjects dosed with tolvaptan on Days 1, 2, 3, and 4, respectively, regardless of status as responder/nonresponder.
- An early termination (ET) sample will be taken for any subject who is receiving tolvaptan.

On Day 2a no PK samples are taken.

For each PK blood sample collected volumes are not expected to exceed 1.2 mL. Total volume per sample may be lower depending on finalization of blood collection supplies.

Serum sodium assessments and other clinically necessary blood samples take priority; therefore, due to restrictions in allowable total daily blood volumes based on local guidelines and subject age, it may not be possible to take more than one PK sample per day. If so, the PK sampling should be changed to:

- Day 1: 2 hours postdose ( $\pm$  5 minutes)
- Day 2: 8 ( $\pm$  2) hours postdose (may be concurrent with serum sodium or other blood sampling)
- Day 3 at trough, ie, predose/24 hours post prior dose (concurrent with serum sodium sample)
- Day 4 at trough, ie, predose/24 hours post prior dose (concurrent with serum sodium sample)

The PK profiles will be evaluated on an ongoing basis to determine the variability between subjects. Based on the findings, PK sampling will continue for as long as necessary to establish suitable estimates of clearance with a 90% CI similar to that observed in the adult populations. Once these estimates are achieved, sampling will be discontinued in subsequent subjects.

For each subject all samples will be collected according to local guidelines and best practices for pediatric care. If a sample is missing due to limitations in allowable blood volumes based on local regulations or local practice this will not count as a protocol deviation.

### **3.7.3.1.2      Sample Handling and Processing**

All blood samples will be shipped to the testing facility for analysis. Detailed handling and shipping instructions are provided in [Appendix 3](#).

### **3.7.3.2      Pharmacodynamic Assessments**

#### **3.7.3.2.1      Fluid Intake**

Fluid intake (both oral and IV) will be measured at the times presented in the schedule of assessments ([Section 3.7.1](#)). The fluid content of foods with significant water content (eg, soup) should be added to the total fluid intake. Fluid intake will be monitored per institutional guidelines.

#### **3.7.3.2.2      Urine Volume**

Urine volume will be determined in urine samples that will be collected at the intervals presented in the schedule of assessments, [Section 3.7.1](#). All urine voids within a collection interval should be kept refrigerated and pooled according to the size of

available collection containers. At the end of the collection interval all samples should be pooled and the urine volume determined.

### **3.7.3.2.3 Urine Chemistry**

Urine chemistry will be determined from pooled urine samples collected for the intervals presented in the schedule of assessments, [Section 3.7.1](#). An aliquot will be taken for each collection interval according to the procedures of the local clinical chemistry laboratory. The list of urine chemistry tests to be conducted is presented in [Table 3.7.4.2.3-1](#).

### **3.7.3.2.4 Palatability and Acceptability Assessment**

A questionnaire will be administered immediately after dosing to assess palatability to rate flavor/taste, smell, sweetness, and overall liking of the study medication. Subjects will also be asked about the ease of swallowing the study medication. Between 15 to 20 minutes after dosing, a questionnaire will be administered to subjects again to assess overall liking of the study medication. This assessment will only be done in subjects aged 3 years to 18 years.

## **3.7.4 Safety Assessments**

Safety will be assessed through the monitoring of AEs, clinical laboratory tests, vital signs, body weight, directed physical examinations, neurological examinations, rescue therapy, and fluid restriction.

The monitoring frequency of safety assessments is at the discretion of the clinical investigator; however, the trial requires the minimum sample collection for all subjects noted in [Section 3.7.1](#) and [Section 3.7.4.2.1](#).

### **3.7.4.1 Adverse Events**

Refer to [Section 5](#), Reporting of Adverse Events.

In addition, active monitoring is required for:

- Absolute serum sodium level  $\geq 145$  mEq/L (mmol/L) or an overly rapid rise in serum sodium level (an increase in serum sodium of  $> 8$  mEq/L [mmol/L] over a 10-hour period,  $\geq 12$  mEq/L [mmol/L] over a 24-hour period, or a rate of increase in serum sodium concentration that the investigator deems too rapid), neurological symptoms, or other signs or symptoms suggestive of osmotic demyelination (see [Section 0](#) for more details).
- Elevations in AST or ALT that are  $\geq 2 \times$  ULN or levels that increase  $\geq 2$  times their previously observed level. If this occurs, a total bilirubin level should also be evaluated. See [Section 3.7.4](#) for more information and [Section 5.4.1](#) for detailed instructions on how this type of event should be captured.
- Worsening symptoms of hyponatremia
- Hypovolemia or hypotension requiring intervention

### **3.7.4.2 Clinical Laboratory Assessments**

#### **3.7.4.2.1 Serum Sodium**

In addition to serum sodium samples obtained for trial qualification and efficacy endpoints, supplemental samples for the purposes of safety assessment only can be obtained using a point of care sodium assessment unit, where available, on Day 1 at 4 to 6 (-1 to + 0.25) hours postdose and at 18 ( $\pm 1$ ) hours postdose. This sodium safety assessment will be repeated at 6 (-1 to + 0.25) and 18 ( $\pm 1$ ) hours postdose each day for the remainder of Treatment Phase A. A point of care assessment unit is preferred since it is expected to reduce overall daily blood volume needed for assessments (expected 0.5 mL for regular blood draws versus up to several drops for a point of care assessment, depending on the device used); however, regular blood draws may be used (especially if they can be combined with standard of care labs).

Additional unscheduled serum sodium assessments may be performed at the discretion of the clinical investigator and other physicians of record, depending on the local standards and subject's clinical condition. All unscheduled serum sodium concentrations collected as part of standard of care will be reported as unscheduled sodium assessments in the electronic case report form (eCRF) through the follow-up sodium assessments.

#### **3.7.4.2.2 Serum Osmolality**

Serum osmolality will be calculated to help guide dosing. Local site personnel will determine serum osmolality using one of the following equations:

- Where Na, glucose, and blood urea nitrogen (BUN) are measured in mg/dL:

$$\text{Serum Osmolality (mOsm/kg)} = 2 \text{ Na} + \text{BUN} / 2.8 + (\text{glucose} / 18)$$

b) Where Na, glucose, and urea are measured in mmol/L:

$$\text{Serum Osmolality (mOsm/kg)} = 2 \text{ Na} + \text{glucose} + \text{urea}$$

### **3.7.4.2.3 Clinical Lab Tests**

[Table 3.7.4.2.3-1](#) presents required clinical laboratory assessments (serum chemistry, hematology, coagulation, urinalysis, and urine chemistry). All clinical laboratory tests will be performed by local laboratories. Serum cortisol and TSH will be measured during screening using the remaining blood sample obtained for serum chemistry. If these results are obtained as part of the standard of care for the subject, a trial-specific sample should be obtained and sent to the local laboratory for analysis per the schedule of assessments ([Section 3.7.1](#)). Urine urea will be measured during screening for calculation of FE urea.

It is recognized that there may be limitations based on age and weight of children for the amount of blood that can be drawn at a single time point, per day, and the overall conduct of the trial. Wherever possible, it is encouraged to combine standard of care samples that would be taken regardless of trial participation with those samples required for the trial.

In case of limited blood or urine volume availability, the bolded assessments in [Table 3.7.4.2.3-1](#) take priority. Serum sodium and liver function tests are essential to the conduct of the trial.

**Table 3.7.4.2.3-1 Clinical Laboratory Tests to be Performed Locally**

Hematology: WBC count with differential RBC count Hematocrit Hemoglobin Mean corpuscular volume Mean corpuscular hemoglobin concentration Platelet count RBC volume distribution width Additional Tests: TSH Serum cortisol Coagulation: International normalized ratio Platelets Prothrombin time Activated partial thromboplastin time	Serum Chemistry: ALT Alkaline phosphatase AST Bicarbonate (or carbon dioxide) Bilirubin, total Urea or Blood urea nitrogen (BUN) Calcium Chloride Cholesterol, total Creatinine Gamma glutamyl transferase Glucose Lactic dehydrogenase Potassium Protein, total Triglycerides Uric acid Efficacy: Serum sodium
Urinalysis: Color Appearance Bilirubin Glucose Ketones Leukocytes Nitrites Occult blood Protein Urobilinogen Microscopic analysis of RBC/WBC (per high powered field) Urine Chemistry: Osmolality Sodium Potassium Creatinine Urea Additional Test: Serum or urine pregnancy test (if applicable)	Drug Screen (all items in urine): Alcohol Amphetamines Barbiturates Benzodiazepines Cannabinoids Cocaine Methadone Opiates Phencyclidine Additional Drug Screen Test: Alcohol (breath)

WBC = white blood cell; RBC = red blood cell.

In case of limited blood or urine volume availability the **bolded** assessments take priority. Serum Sodium and liver function tests are essential to the conduct of the trial.

### 3.7.4.2.4 Monitoring of Liver Transaminases

Long-term use of tolvaptan has demonstrated the potential to cause a clinically significant elevation in laboratory tests of liver function. Based on previous research in the adult

polycystic kidney disease population, the expected onset of the elevation, if it occurs, is between 3 and 14 months of chronic treatment with tolvaptan.

For a subject who experiences an elevation in AST or ALT that is  $\geq 2 \times$  ULN or whose levels increase  $\geq 2$  times their previous observed value, a total bilirubin level should also be evaluated. These elevated values should be confirmed by retesting. If total bilirubin is  $\geq 2 \times$  ULN or  $\geq 2$  times their previous observed value, an immediately reportable event (IRE) form with all values listed should be completed and also reported as an AE on the eCRFs. See [Section 5.4.1](#) for detailed instructions on how this type of event should be captured.

### **3.7.4.3 Physical Examination**

Full and directed physical examinations will be performed and documented according to the schedule of assessments ([Section 3.7.1](#)). The initial physical examination should be a full physical. Subsequent physical examinations can be directed physical examinations that are focused on hyponatremia-related signs and symptoms as well as any major changes from baseline.

The principal investigator or his/her appointed designee is primarily responsible to perform the physical examination. If the appointed designee is to perform the physical examination, he/she must be permitted by local regulations. Whenever possible, the same individual should perform all physical examinations for a given subject. Any condition present at the post-treatment directed physical examination that was not present at Screening should be documented as an AE and followed to a satisfactory conclusion.

Full physical examination assessments should include assessments of all major body systems, including but not limited to, ears, nose, and throat, the thorax area, abdomen, urogenital, extremities, and skin and mucosae. Directed physical examinations should be focused on hyponatremia-related signs and symptoms as well as any major changes from baseline. Physical examination will include a fontanelle assessment as age appropriate. Neurological examinations will be performed in an age-appropriate manner per [Section 3.7.4.3.1](#).

Body weight will be measured predose each day throughout Treatment Phase A, Treatment Phase B and at each clinic visit in Follow-up Phase C, as possible. Every effort should be made to ensure that body weight measurements are performed in a reproducible and consistent manner. Body weight measurements should be performed at the clinical site always using the same scale. Subjects should wear the same type of clothes at each measurement, preferably a gown and no shoes. All body weight measurements should be taken post void.

### **3.7.4.3.1      Neurological Examination**

A neurological examination will be performed as part of the directed physical exam per the schedule of assessments ([Section 3.7.1](#)). It will include an evaluation of mental status, cranial nerves, muscle tone, muscle strength/symmetry, reflexes, neonatal primitive reflexes, sensory system, gait, and finger to nose, as age appropriate.

### **3.7.4.4      Tanner Staging**

Tanner Staging must be completed together with the physical examination by the same trial-affiliated clinician in the most inconspicuous manner for the subject as possible.

Tanner Staging could be completed by the trial affiliated pediatrician or family practitioner (additionally physician's assistant or nurse practitioner where licensing permits). Sites should make attempts to have examiners of both sexes. Attempts should be made to have the examination performed by the same sex personnel as the subject. Otherwise, trial-affiliated personnel of the same sex as the subject (ie, nurse) should be in the same examination room as the subject.

Tanner Staging assessment consists of 2 domains (pubic hair and breast development) for girls and 3 domains (pubic hair, penis development, and testes development) for boys.

The Tanner Staging assessment as a reference for the completing clinician is included in [Appendix 4](#). The investigator will arrive at a single score summarizing the domains (not individual domain scores) when evaluating the subject.

### **3.7.4.5      Vital Sign Assessments**

Vital signs (including supine blood pressure, heart rate, respiratory rate, and temperature) will be assessed at time points according to [Section 3.7.1](#) of this protocol. Supine vital signs will be taken when the subject has been lying down (bed positioned < 45 degree angle) for  $\geq$  3 minutes. All assessments for vital signs should be performed around the time of the formal hyponatremia assessment (sodium blood draw) during Screening, Treatment Phase A and Treatment Phase B and anytime during the Follow-up Period consistent with the timing of other trial assessments. All vital sign assessments should be performed predose and prior to the blood draw at the nominal time point.

### **3.7.4.6      Electrocardiogram Assessments**

One ECG will be recorded at screening, prior to any blood draws. Twelve-lead ECGs will be recorded with the subject supine and at rest (for at least 10 minutes). Heart rate, PR interval, QRS duration, and QT interval will be recorded. The principal investigator or designee will review, sign, and date each ECG reading. Any abnormalities should be reported as part of the medical history. Whenever possible, the same reviewer should

evaluate, sign, and date the ECGs. A paper copy of the ECG will be sent for storage to a central ECG storage facility.

#### **3.7.4.7      Hyponatremia History**

Each subject's hyponatremia medical history will be recorded at screening. The hyponatremia history should include the etiology of subject's hyponatremia (including assessments per [Section 3.2.4.2](#)) and what treatment was administered prior to trial enrollment. Symptoms potentially attributable to hyponatremia should be specifically assessed for prior history. The hyponatremia assessment at Screening will consist of documentation of hyponatremia etiology (eg, HF, hepatocellular disease [including cirrhosis], SIADH/other), prior fluid intake and output, and prior hyponatremia treatment, ie, fluid restriction, if applicable. A detailed history specific to etiology of hyponatremia will also be recorded.

#### **3.7.4.8      Volume Status Assessment**

Volume status will be assessed every 6 hours prior to trial entry and every 6 hours during Treatment Phase A.

#### **3.7.4.9      Vital Status**

An assessment of vital status will be conducted on subjects who terminate prior to the last study visit, and do not withdraw consent for continued telephone contact. The telephone contact will be made 14 days post-last dose, and will be conducted with a reliable informant; either the subject and/or the parent/guardian, per investigator discretion. Vital status collected and recorded will be:

- Subject alive
- Subject deceased (date of death, cause of death)

#### **3.7.5      End of Trial**

The End of Trial Date is defined as the last Date of Contact or the Date of Final Contact Attempt from the Post-treatment Follow-up eCRF page for the last subject completing or withdrawing from the trial.

#### **3.7.6      Independent Data Monitoring Committee**

An independent data monitoring committee (IDMC) will be established for this trial. This committee will meet on a regular basis to ensure the safe and ethical treatment of trial subjects, ensure the scientific integrity of the trial, and to ensure the trial is conducted within the bounds of ethical medical practice. It may make recommendations

to the sponsor and trial steering committee to amend or terminate the trial based on grounds of safety, futility, or greater than expected efficacy as defined by the accepted statistical practices and procedures to be detailed in their charter. The specific duties of the IDMC will be detailed in a separate IDMC charter document.

### **3.8      Stopping Rules, Withdrawal Criteria and Procedures**

#### **3.8.1      Entire Trial or Treatment Arm(s)**

If the sponsor terminates or suspends the trial for safety or unanticipated other reasons, prompt notification will be given to investigators, IRBs/IECs, and regulatory authorities in accordance with regulatory requirements.

#### **3.8.2      Individual Site**

The investigator will notify the sponsor promptly if the trial is terminated by the investigator or the IRB/IEC at the site.

#### **3.8.3      Individual Subject Discontinuation**

If a subject discontinues from the trial prematurely, the reason must be fully evaluated and recorded appropriately in source documents and the eCRF. If the subject is being withdrawn because of an AE, that AE should be indicated as the reason for withdrawal.

All subjects have the right to withdraw at any point during treatment without prejudice. The investigator can discontinue a subject's participation in the trial at any time if medically necessary. In addition, subjects meeting the following criteria following the first dose of tolvaptan must be withdrawn from the trial:

- a) Occurrence of any AE, intercurrent illness, or abnormality in a laboratory assessment which, in the opinion of the investigator, warrants the subject's permanent withdrawal from the trial;
- b) Treatment with a prohibited concomitant medication other than the use of appropriate medications for the treatment of AEs under direction of the investigator;
- c) Subject noncompliance, defined as refusal or inability to adhere to the trial schedule or procedures (eg, blood draw requirements); see [Section 3.12](#), Subject Compliance);
- d) At the request of the subject, investigator, OPDC or designee, or regulatory authority;
- e) Subject becomes pregnant; or
- f) Subject is lost to follow-up.

Subjects who have clinically relevant TSH or cortisol levels may not respond properly to tolvaptan and will be withdrawn from the trial.

In addition, subjects meeting the following criteria should have results confirmed with a repeat test (if the result is confirmed, the medical monitor should be contacted to consider options of down-titration, dose interruption, concomitant medication adjustment, fluid supplementation, and/or withdrawal):

- Subject's serum sodium level increases by  $> 8$  mEq/L [mmol/L] in any 10-hour period following dosing on Day 1
- Subject's serum sodium level increases by  $\geq 12$  mEq/L [mmol/L] in the 24-hour period following dosing
- At any time after dosing, the subject's serum sodium is  $\geq 145$  mEq/L [mmol/L]

Subjects who require IV infusion of isotonic or hypertonic saline for hyponatremia or who receive another approved/off-label therapy (rescue therapy) for hyponatremia before completion of the trial will be withdrawn from trial treatment; these subjects should continue to Phase C to be followed. Subjects, who are randomized to the Early Withdrawal group, whose serum sodium level declines by  $\geq 4$  mEq/L (mmol/L), or whose overall clinical condition requires further treatment to increase serum sodium level will be treated per the investigator's preferred standard of care. Any intervention intended to raise serum sodium during the first 48 hours of the Early Withdrawal phase (including fluid restriction) will be defined as rescue therapy. The subject will be considered to have reached their clinical endpoint, and their data will be censored from that time forward.

The sponsor and the medical monitor should be notified promptly when a subject requires treatment other than trial treatment for the purpose of raising serum sodium. Subjects receiving rescue therapy are to continue to be monitored per protocol (to discharge or death). Subjects terminated prior to completion will not be re-enrolled.

The investigator will notify the sponsor promptly when a subject is withdrawn.

When a subject or parent/legal guardian or legally responsible representative decides to withdraw from the trial they will be asked to indicate whether they wish to discontinue from the trial as a whole, or still allow telephone contact. If they agree to continued telephone contact, they will be contacted 14 days after the last study visit for vital status ([Section 3.7.4.9](#)).

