- In Treatment Phase A, PK samples should be collected on Day 1 at 2 hours ( $\pm$  5 minutes) and 8 hours post-first dose and assessed at trough (24 [ $\pm$  4] hours post-first dose). A PK sample should be assessed on Day 2 at trough (24 [ $\pm$  4] hours post-previous dose, but prior to the next dose). On Day 2a no PK samples are taken.
- In Treatment Phase B, PK will be assessed in subjects continuing treatment with tolvaptan (Late Withdrawal group and nonresponders continuing on tolvaptan) at trough (24 [ $\pm$  4] hours post-previous dose, but prior to the next dose) on Days 3 and 4.

If there are restrictions in the allowable total daily blood volumes per local guidelines and subject age, the PK assessment schedule should be the following:

- Day 1 at 2 hours postdose ( $\pm$  5 minutes)
- Day 2 at 8 ( $\pm$  2) hours postdose (may be concurrent with serum sodium or other blood sampling)
- Days 3 and 4 at trough (24 [ $\pm$  4] hours post-previous dose, but prior to the next dose and concurrent with serum sodium sample)

qThe tolvaptan dose will be titrated based on serum sodium levels as described in [Section 3.2.4](#).

rOptional swallow test for subjects for whom it is unknown if they are able to swallow tablets, at the investigator's discretion.

sVital status will be collected at 14 days post-last dose only for subjects who discontinued early and did not withdraw consent.

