### **5.4.1 Liver Transaminase Elevations**

Management of abnormal liver function test results should be based on the investigator's clinical judgment. A liver function test result that is  $2 \times$  ULN is generally accepted as a medically significant occurrence across various medical disciplines.

For a subject that experiences an elevation in AST or ALT that is  $\geq 2 \times$  ULN or whose levels increase  $\geq 2$  times their initial baseline value in subjects with an elevated baseline value, a total bilirubin level should also be evaluated. If the total bilirubin is  $\geq 2 \times$  ULN or  $\geq 2$  times their baseline value in subjects with an elevated baseline value, an IRE form with all values listed should be completed and also reported as an AE on the eCRFs.

The following guideline for repeat testing may be used by investigators as a reference for any subject with an ALT or AST  $\geq 2 \times \text{ULN}$ :

- 1) ALT, AST, alkaline phosphatase, and total bilirubin should be repeated within 48 to 72 hours (needed to confirm abnormalities and determine if they are increasing or decreasing).
- 2) Inquiries should be made about symptoms (fatigue, nausea, vomiting, right upper quadrant pain or tenderness, fever, and/or rash) and signs like jaundice, yellowish discoloration of sclera, etc.
- 3) If discharged or transferred, the subjects should be retested locally and results given to the investigator immediately, along with that laboratory's normal ranges.
- 4) Close observation is required if symptoms persist or repeat testing shows ALT or AST  $\geq 3 \times \text{ULN}$  for subjects with normal baseline measures OR 2-fold increases above baseline values for subjects with elevated values before drug exposure. If close monitoring is not possible, the drug should be interrupted until such monitoring is possible or the drug should be permanently discontinued.
- 5) All trial subjects with evidence of possible drug-induced liver injury should be followed until all abnormalities return to normal or to the baseline state.

Close observation may involve:

- 1) Repeating liver enzymes and serum bilirubin tests 2 or 3 times weekly.
- 2) Frequency of retesting can decrease to once a week or less if abnormalities stabilize or if the trial drug has been interrupted/discontinued and the subject is asymptomatic.
- 3) Obtaining a more detailed history of symptoms and prior or concurrent diseases.

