#### **5.4.1.1 Criteria for Discontinuation Due to Liver Transaminase Elevations**

A subject must be discontinued from the trial on confirmation of any of the following criteria:

- 1) ALT or AST  $\geq 8 \times$  ULN
- 2) ALT or AST  $\geq 5 \times$  ULN for more than 2 weeks
- 3) ALT or AST  $\geq 3 \times$  ULN AND (total bilirubin  $\geq 2 \times$  ULN or INR  $> 1.5$ )
- 4) ALT or AST  $\geq 3 \times$  ULN with appearance of fatigue, nausea, vomiting, right upper quadrant pain or tenderness, fever, rash, and/or eosinophilia ( $> 5\%$ ) and signs of jaundice

If there is any question about how to proceed with a particular subject's case, do not hesitate to contact your regional medical monitor to discuss. The FDA has issued a guidance for industry regarding this topic. This guidance is not specific to hyponatremia. Otsuka is integrating many of the recommendations in this guidance into all of its clinical research programs. Links to this guidance and information from the FDA regarding drug-induced liver injury are provided in the references. 

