## **5.7 Follow-up of Adverse Events**

For this trial, information on AEs will be followed for up to 14 days post-last dose for all subjects or until resolution, whichever is longer.

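### Children withdrawn from the trial for a safety or laboratory reason lose the scheduled 7-day assessments and 14-day adverse-event enquiry that rescued children keep, and the protocol contradicts itself on this

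*Protocol*

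**What the plan says.** **Exit from the trial.** Protocol 3.8.3 states that "subjects meeting the following criteria following the first dose of tolvaptan must be withdrawn from the trial". Item (a) covers an adverse event, intercurrent illness or laboratory abnormality that, "in the opinion of the investigator, warrants the subject's permanent withdrawal from the trial". The same section, and footnote o of Table 3.7-1, also withdraw from the trial any child with clinically relevant TSH or cortisol. Those results are not needed for eligibility, so such a child may already have been dosed. For liver tests, 5.4.1.1 states: "A subject must be discontinued from the trial on confirmation of any of the following criteria".

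**Exit from treatment only.** Under 3.8.3, children who need rescue "will be withdrawn from trial treatment; these subjects should continue to Phase C to be followed". Section 3.2.4.2 agrees and gives collection of safety information as the purpose.

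**What early termination brings.** Section 3.7.1.4.1 gives one visit, at 72 hours post-last dose or at ET, plus monitoring for up to 3 days after the last dose. Table 3.7-1, footnote s, adds: "Vital status will be collected at 14 days post-last dose only for subjects who discontinued early and did not withdraw consent". Section 3.7.4.9 limits the recorded content to alive, or deceased with date and cause.

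**What applies to everyone.** Section 3.1.1.3 assigns the 72-hour, 7-day and 14-day contacts to all subjects. Under 5.7, "information on AEs will be followed for up to 14 days post-last dose for all subjects or until resolution, whichever is longer". Section 5.7.2 requires active SAE monitoring over the same period. Section 3.10 recognises children who stop tolvaptan early but stay in the trial.

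**The concern.** Stopping a drug and leaving a trial are different decisions. The protocol separates them for rescue but not for children removed on safety or laboratory grounds. A child taken off for an adverse event therefore has fewer scheduled assessments than one taken off for inadequate sodium control. The planned 7-day sodium and neurological examination are there to detect relapse after stopping and signs suggestive of osmotic demyelination. The 14-day contact is there to pick up new events. If those data are missing mainly in children who left for a safety reason, the missingness is related to the outcome, and the safety tables rest on an uneven observation period. Sites also face two sets of instructions and may apply either.

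**Working it through.** No sample size, power or rate enters, so the check compares provisions.

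**1. Scheduled contacts after stopping** (Table 3.7-1; 3.7.1.4.1 to 3.7.1.4.3; 3.7.4.9)

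| | Rescued: leaves treatment | Withdrawn from the trial |
|---|---|---|
| First visit | 72 hours post-last dose | ET visit |
| 7 (+1) days: sodium, neurological and physical examination, vital signs, weight, QoL, pregnancy test if applicable | Yes | Not scheduled |
| 14 days | New or ongoing AEs, medications | Vital status only, if contact is permitted |
| Total | 3 contacts | 1 visit and 1 optional call |

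The ET visit is itself full: vital signs, weight, examinations, sodium, laboratory panel, urinalysis, AEs and medications. The loss lies in what should come after it.

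**2. Length of the gap for a child withdrawn during dosing.** The last scheduled sodium and neurological examination for a rescued child is 7 days post-last dose. If the additional monitoring runs its full 3 days, the difference is 7 − 3 = 4 days. If the ET visit falls on the day of the last dose and no monitoring follows, it is 7 − 0 = 7 days.

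**3. The liver criteria.** After screening, Table 3.7-1 schedules liver tests only at 72 hours post-last dose or at ET. At the 72-hour draw dosing has ended, so leaving the trial cannot stop drug; it can only remove later visits. Section 5.4.1 suggests repeat testing within 48 to 72 hours, so confirmation would come about 3 + 2 = 5 to 3 + 3 = 6 days post-last dose, before the 7-day visit. If an ET visit is held then, little sodium or examination time is lost and the main loss is the 14-day enquiry. Criterion 2 needs elevation for more than 14 days, whereas dosing lasts at most 5. Unscheduled tests can still meet the other criteria during dosing.

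**4. What Section 5 keeps.** AEs are followed for at least 14 days or to resolution (5.7). Unresolved nonserious AEs get contacts at least every 4 weeks (5.7.1). SAEs are followed until baseline, normal or explained (5.3), and hyponatremia-related events until resolved or stable (5.3.1.2). For the liver, 5.4.1 says: "All trial subjects with evidence of possible drug-induced liver injury should be followed until all abnormalities return to normal or to the baseline state". None of these provisions schedules a 7-day sodium or neurological examination, and none turns the 14-day vital-status call into an enquiry about new events.

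**5. Call timing.** The vital-status call is 14 days post-last dose in Table 3.7-1, 3.7.1.4.1 and 3.7.4.9, but 14 days after the last study visit in 3.8.3.

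**6. Analysis impact.** Protocol 3.5.3.1 lists the sodium change from 24 hours to 7 days post-last dose for all subjects. SAP 5.1.8.3 restricts it to the Phase B Efficacy Sample for responders. As analysed, it loses data only from randomized responders who are withdrawn from the trial.

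**The case against.** The strongest reply is that Section 5 governs event follow-up and exempts nobody. A child withdrawn for a safety event has open-ended follow-up of that event, and possible liver injury is followed to normal or baseline. Footnote s can be read as saying who receives a vital-status call, not as limiting those children to it. Item (a) applies only where the investigator judges permanent trial withdrawal to be warranted. Section 5.4 speaks of stopping tolvaptan, not of leaving the trial, when liver injury is suspected, and 3.10 allows a child to stop drug and remain.

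Much of this stands. A reader might infer that these children get nothing beyond an ET visit and an alive-or-dead call, or that they are the least observed in the trial. Section 5 and the 3 days of monitoring rule that out. A reader might also take a rapid sodium rise as the typical case. It is not a mandatory-withdrawal criterion: after a confirmed value, "the medical monitor should be contacted to consider options of down-titration, dose interruption" and other measures, of which withdrawal is only one.

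The reply does not supply the missing scheduled items. Neither 3.8.3(a) nor 5.4.1.1 points to the category in 3.10. The duties in 5.7 and 5.7.2 have no matching procedure for early-terminated children, whose described 14-day contact collects vital status. The provisions relied on in the reply are one half of the contradiction.

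**Conclusion.** The point holds as an unreconciled contradiction with a limited, specific loss: the 7-day sodium, the 7-day neurological and physical examinations, and the 14-day enquiry about new AEs and medications. For a withdrawal during dosing, the gap in scheduled sodium and examination is about 4 to 7 days; for a liver finding at the 72-hour draw it may be smaller. This assumes that the ET column replaces the 7-day and 14-day columns, which is the natural reading of the schedule but is contradicted by 3.1.1.3.

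The documents give no withdrawal rate, so no number of children can be stated. Nor do they support a material effect on the primary endpoint: SAP 5.1 records early termination with very low enrollment and reduces efficacy to summary statistics. Safety analysis remains (SAP 5.2), and with few children each incomplete record weighs more. This is a worthwhile, inexpensive improvement, not a flaw that invalidates the trial.

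**What to change.** Reconcile 3.8.3, 5.4.1.1, Table 3.7-1 footnotes o and s, 3.7.1.4.1 and 3.7.4.9 with 3.1.1.3, 3.10, 5.7 and 5.7.2. State that a child stopped for a safety or laboratory reason completes the Phase C assessments already in the schedule (72 hours, 7 days and the 14-day AE and medication contact) unless consent is withdrawn. Keep the vital-status-only call for families who refuse further visits, and time it from one reference point throughout. Leave every criterion for stopping drug as it is; the change concerns data collection after stopping.

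The cost is amendment wording and a few more attended visits for children who are off drug. No new assessment is created. As the SAP reports early termination, the practical value now lies mainly in any further use of this protocol text.
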